- b) **Block Quality:** Achieving an inability to sense cold ice-water in the cutaneous distribution of the brachial plexus trunk distal to the block within 30 minutes will be considered a **successful nerve block** preoperatively. If the patient has an inability to sense cold ice-water in the cutaneous distribution of the brachial plexus trunk distal to the block within 30 minutes will be considered a **successful nerve block** postoperatively. Anything less will be considered a **failed nerve block**.

12) Secondary Outcomes:

- i) Return of sensory function in the blocked area of the limb.
- ii) Return of motor function in the blocked area of the limb.
- iii) Post-op Nausea and vomiting before discharge
- iv) Nausea and Vomiting after discharge
- v) Changes in Blood Pressure (BP) in the PACU defined as any blood pressure +/- 20% of patient's baseline (either BP on admission if no clinic BP is documented, or most recent clinic BP as documented if that exists)
- vi) Changes in Blood Pressure in Second Stage defined as any blood pressure +/- 20% of patient's baseline (either BP on admission if no clinic BP is documented, or most recent clinic BP as documented if that exists)

Motor Block Scale Table

Muscle function level	Scale	
	Grade	Percent of normal
No evidence of contractility	0	0 %
Slight contractility, no movement	1	10 %
Full range of motion with gravity eliminated	2	25 %
Full range of motion against gravity	3	50 %
Full range of motion against gravity, some resistance	4	75 %
Full range of motion against	5	100 %

gravity, full resistance		
--------------------------	--	--

Definitions:

- a) Duration of Analgesic Block
 - i) Time from nerve block-needle withdrawal until the **time reported by the patient** that they first had awareness of painful sensation returning anywhere in the surgically operated upon area of the limb.
 - ii) Patient will be given a form to write time down as it occurs.
 - iii) They are expected to write down the date and time (hour and minute) they first perceive pain in the arm anywhere in the surgical area. (even if they wake up from sleep and first notice pain there).
 - iv) They will be telephoned within three days from the block to gather the data from the patient.
 - v) If they cannot find the form or did not write the date and time down, we will then use the date and time the patient recalls from memory.
- a) Duration of Sensory Block

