 - i) Time from nerve block-needle withdrawal until the **time reported by the patient** that they first had awareness of tactile (light touch) sensation returning anywhere in the blocked area. Patients will be given a form to write time down as it occurs. They are expected to write down the date and time (hour and minute) they first felt sensation return to the blocked area (even if they wake up from sleep and first notice sensation returned).
 - ii) They will be telephoned within three days from the block to gather the data from the patient.
 - iii) If they cannot find the form or did not write the date and time down, we will then use the date and time the patient recalls from memory.
- a) Approximate Duration of Motor Block
 - i) Time from nerve block-needle withdrawal until the **time reported by the patient** that, with the arm of the blocked extremity, they are able to **flex their bicep**. Patient will be given a form with a diagram and instruct them prior to sedation and placing the block. They will write the time down when they are able to achieve this outcome. They are to write down the date and time (hour and minute) they were first able to flex their bicep on the blocked limb.
 - ii) They will be telephoned within three days to gather the time from the form.
 - iii) If they cannot find the form or did not write the data down, we will then use the time the patient recalls from memory.
- a) Patient Satisfaction with the block
 - i) Patients will be asked the question: "Would you want a nerve block again if you needed a similar surgery in the future?" Yes / No

Secondary Outcomes Table

Did patient have nausea before discharge	
Yes	No
Did patient have vomiting before discharge	
Yes	No
Did patient have nausea after discharge (72 hours)	
Yes	No
Did patient have vomiting after discharge (72 hours)	
Yes	No
Did the patient have +/- 20% deviation of baseline Blood pressure in PACU from admission	
Yes	No
Did the patient have +/- 20% deviation of baseline Blood pressure in Second Stage Recovery from admission	
Yes	No

2) Study Background Information:

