- d) Using the above parameters, a sample size is 40 per group with 4 total groups calculates to a sum of 160 subjects while using 90% power and 0.05 type I error rate.

9) Safety Monitoring:

- a) An Anesthesiology Faculty member who is not involved in the study will act as safety monitor and will review the data and any complications when half of the patients (n = 80) have been completed.

10) Stopping Rules:

- a) Any incidence of patient complications that occur with an incidence higher than published data for the following complications for peripheral nerve blocks will be enough cause for the Safety Monitors to stop the study(31, 32). Numbers in parentheses below are the highest incidence reported in the referenced article for peripheral nerve block complications. The highest incidence of complications was reported to be from the supraclavicular block, which we will not be performing. We are relying on results reported from our own regional anesthesia follow-up clinic. This is a clinic developed here to see patients with troublesome complications of peripheral nerve blocks. The complication rates have been reviewed and studied since the clinic inception over 4 years ago(33). We are erring on the side of caution by using higher complication rates of the supraclavicular adverse event reports.
- b) Published Peripheral Nerve Block Complication rates:
 - i) Seizure (26.3/10,000)
 - ii) Cardiac arrest (Code Blue) (15.9/10,000)

- iii)** Respiratory Failure (15.9/10,000)
- iv)** Peripheral neuropathy (32/10,000)
- v)** Patient death (15.9/10,000)

References:

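### Peripheral neuropathy is a stopping event, but the protocol lists no question that would find a partial deficit at home, so a case that decides the rule may go unrecorded

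*Combined protocol and SAP*

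**What the plan says.** Section 10 (Stopping Rules), item a, lets the safety monitors stop the study for "Any incidence of patient complications that occur with an incidence higher than published data". Item b lists five events with rates, among them "Peripheral neuropathy (32/10,000".

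The data that patients supply are set out in the Definitions and the Secondary Outcomes Table: times of return of pain, light touch and biceps flexion; one satisfaction question; nausea and vomiting before and after discharge; and blood pressure deviations in the two recovery stages. Rescue blocks in the PACU are also counted (Techniques, item l). For the return times the plan is: "They will be telephoned within three days from the block to gather the data from the patient". The longest outcome window stated is that of items such as "Did patient have nausea after discharge (72 hours". No later contact is scheduled.

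Three provisions bear on cases once they exist. Techniques, item k, requires stopping events to be reported to the safety monitors the same day. Section 9 (Safety Monitoring) has a monitor "review the data and any complications when half of the patients (n = 80) have been completed". Section 10 also describes a local follow-up clinic: "This is a clinic developed here to see patients with troublesome complications of peripheral nerve blocks". No visit of trial patients to that clinic, and no report from it to the trial, is described.

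**The concern.** A stopping rule is only as good as the way its events are found. Seizure, cardiac arrest or respiratory failure soon after the block would occur under monitoring. A neuropathy would show itself at home, after the block should have worn off, and the protocol lists nothing that asks about it. If a case is not volunteered, the monitor at the half-way review sees no neuropathy and cannot tell an absence of cases from an absence of enquiry. The trial tests three additives that the background section says are not FDA approved for perineural use, so an increase in neuropathy is one of the things the rule exists to catch.

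**Working it through.** **1. What the listed items can detect.** Neuropathy is set against each item that bears on it.

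- Sensory return is the first light touch felt at any point of the blocked region. A patient still numb throughout has no time to give, and that would surface at the call. A patient numb in one territory gives an ordinary time and looks recovered.
- Motor return is the ability to flex the biceps. Weakness in another muscle is not recorded.
- No rule turns a missing return time into a suspected neuropathy. A time that was not written down is taken from memory, and section 8, item b, assumes that outcomes are observed on every patient.
- Same-day reporting and the review at 80 patients act on cases already known. Neither says how a case is found.

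**2. How many cases meet the rule.** Inputs: benchmark p = 32/10,000 = 0.0032 (section 10); review at n = 80 (section 9); total n = 160 (section 8, 40 × 4). The benchmark is a cited value and cannot be re-derived from the documents.

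- 1/80 = 125 per 10,000, above 32.
- 1/160 = 62.5 per 10,000, above 32.
- 1/0.0032 = 312.5, so a single case would fall within the benchmark only from 313 patients.

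In this trial the criterion is therefore met by any one recorded case.

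**3. Chance of recording none at the benchmark rate.** With capture probability s, P(0) = (1 − 0.0032 × s)^n. The documents give no capture rate; the values of s are assumptions.

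| Capture s | n = 80 | n = 160 |
|---|---|---|
| 100% | 77.4% | 59.9% |
| 50% | 88.0% | 77.4% |
| 25% | 93.8% | 88.0% |
| 10% | 97.5% | 95.0% |

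With full capture, the expected count is 80 × 0.0032 = 0.256 and 160 × 0.0032 = 0.512. The chance of at least one case is 1 − 0.774 = 22.6% and 1 − 0.599 = 40.1%. Missing half the cases adds 10.6 points to P(0) at 80 (88.0 − 77.4) and 17.5 points at 160 (77.4 − 59.9).

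**4. Chance of recording none if the true rate is raised.** Assume five times the benchmark: 5 × 0.0032 = 0.016, so P(0) = (1 − 0.016 × s)^n.

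| Capture s | n = 80 | n = 160 |
|---|---|---|
| 100% | 27.5% | 7.6% |
| 50% | 52.6% | 27.7% |
| 25% | 72.6% | 52.7% |

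With full capture, 160 patients would very probably show at least one case. With a quarter captured, it is about an even chance that none is recorded.

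**The case against.** A reader might infer that the rule will read zero because nobody asks, or that the planned data cannot reach it. The documents support neither.

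- At the protocol's own rate, zero is the likeliest count even with perfect capture. Rarity and sample size account for most of it.
- The call does collect sensory and motor return times, so a complete failure to recover would come to light.
- Known cases have a route: same-day reporting, the review at 80 patients and a specialist clinic. The Consent section also says that enrolled patients are followed, though it gives no contact or period.
- The call form itself is not in the text supplied, and only the three return times are expressly tied to the call. The claim must be that the protocol lists no such item, not that no form contains one.
- Adding questions has its own risk. Since one case meets the criterion, a single early answer that reflects residual block could trip it. The benchmark may also rest on a different way of finding cases, which the documents do not show.

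All of this stands, and it limits the point. It does not remove it: partial deficits remain unasked about, the reporting routes start only when somebody already knows, and the clinic sees those who come to it.

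**Conclusion.** The point holds in a limited form. Neuropathy is an undefined stopping event with no listed question and no contact after the three-day call, so a partial or later deficit may go unrecorded, and one such case is enough to decide whether the rule is met. At the benchmark rate the gap moves the result only moderately. Its main cost is lost ability to see a raised rate: at five times the benchmark, the chance of recording no case in 160 rises from 7.6% to 27.7% or 52.7%. Those figures rest on assumed values for the raised rate and for capture (50% and 25%), on independent patients, and on the benchmark as cited. Even full capture would leave limited reassurance: zero cases gives a one-sided 95% upper bound of 1 − 0.05^(1/80) = 3.7% at 80 and 1 − 0.05^(1/160) = 1.9% at 160. The change should be made because it is cheap and concerns safety; the arithmetic does not show that the rule is unworkable.

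**What to change.** - Add two yes/no questions to the existing call: any remaining numbness or tingling, and any remaining weakness, in the blocked limb. Record the date and time of the call.
- Treat a sensory or motor return time that is missing because function has not returned as a yes. Keep it distinct from a time that was merely not written down.
- Send every yes to the safety monitor.
- Ask the existing follow-up clinic to report any study patient it sees.
- Have the sponsor define in advance when a yes or a clinic report counts as a neuropathy case, so that residual block is not counted against 32/10,000, and note that the benchmark may come from a different method of finding cases.

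The cost is two lines on a call already planned, a written case definition, and an arrangement with a clinic that already exists; the documents do not say what permission or staff time that arrangement would need. Some early yes answers will be residual block and must be reviewed, although patients with any neuropathy or diabetes are already excluded, which makes a yes more likely to be new. Later cases would still be found only through the clinic.
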